#### 9.4.3 Management of Proteinuria

Regular assessment for proteinuria should be conducted as detailed in the Schedule of Procedures/Assessments (Table 5) and as clinically indicated. Guidelines for assessment and management of proteinuria are summarized as follows:

- Initial episode of proteinuria: If proteinuria  $\geq$  2+ is detected on urine dipstick testing, lenvatinib and everolimus will be continued and a 24-hour urine collection for total protein will be obtained as soon as possible within 72 hours to verify the grade of proteinuria. Grading according to CTCAE v4.03 (Appendix 6) will be based on the 24-hour urine collection for total protein result. Dosing will be managed based on the grade of proteinuria according to Table 2.
- Second and the subsequent episode of proteinuria : If proteinuria 3+ or 4+ is detected on urine dipstick testing, lenvatinib and everolimus will be continued and a 24-hour urine collection for total protein will be obtained to verify the grade of proteinuria. Dosing will be managed based on the grade of proteinuria according to Table 2. If proteinuria  $\geq$ 2+ continues and is clinically indicated, a 24-hour urine collection for total protein will be obtained to verify the grade of proteinuria.
- Urine dipstick testing for subjects with proteinuria  $\geq$  2+ should be performed every 2 weeks (on Day 15 or more frequently as clinically indicated) until the results have been 1+ or negative for 3 consecutive months. If a new event of proteinuria  $\geq$  2+ occurs, the subject must resume the Day 15 urine dipstick testing for evaluation of proteinuria until results are 1+ or negative for 3 consecutive months.

#### 9.4.4 Management of Hepatotoxicity

Regular monitoring of liver function tests (eg, alanine transaminase [ALT], aspartate transaminase [AST], bilirubin levels) should be conducted as detailed in the Schedule of Visits and Procedures (Table 5) and as clinically indicated. If signs occur indicating a decrease in liver function by 1 grade or more from baseline, the instructions contained in Table 2 of the protocol should be followed, "Study Treatment Dose Reduction and Interruption Instructions". Appropriate supportive care should be provided together with close monitoring. If hepatic failure occurs both lenvatinib and everolimus must be discontinued.

#### 9.4.5 Management of Thromboembolic Events

Subjects should be advised to pay attention to the symptoms suggestive of venous thromboembolic events, which include acute onset of dyspnea, chest pain, cough, hemoptysis, tachypnea, tachycardia, cyanosis, DVT signs including lower-extremity swelling, redness and warmth to touch or tenderness. In case any of these signs or symptoms appears, subjects should be instructed to report such signs and symptoms promptly to the treating physician. If a thromboembolic event is confirmed, instructions contained in Table 2 of the protocol should be followed, "Study Treatment Dose Reduction and Interruption Instructions." Appropriate supportive care should be provided together with close monitoring. If a subject experiences life-threatening (Grade 4) thromboembolic reactions, including pulmonary embolism, both lenvatinib and everolimus must be discontinued.

#### 9.4.6 Management of Posterior Reversible Encephalopathy Syndrome (PRES)

In clinical studies with lenvatinib, events of posterior reversible encephalopathy syndrome (PRES) were reported in less than 1% of lenvatinib-treated subjects. PRES is a neurological disorder that can present with headache, seizure, lethargy, confusion, altered mental function, blindness, and other visual or neurological disturbances. Mild to severe hypertension may be present. MRI is necessary to confirm the diagnosis of PRES. Appropriate measures should be taken to control blood pressure. In subjects with signs or symptoms of PRES, dose interruptions, reductions, or discontinuation of both lenvatinib and everolimus may be required per instructions included in Table 2.

#### 9.4.7 Management of Interstitial Lung Disease

Interstitial lung disease (pneumonitis, lung disease, lung infiltration, alveolitis, pulmonary alveolar haemorrhage and pulmonary toxicity) is a frequently reported adverse reaction when treated with rapamycin derivative including everolimus, and it can be fatal in rare cases. If breathing conditions of unknown cause are observed, the subject must be appropriately examined to rule out possible causes such as infection, neoplasm, and other nondrug related conditions to confirm diagnosis of lung disease.

Following procedures should be followed when determining dose of lenvatinib and everolimus for subject with lung disease.

- Radiology findings indicate lung disease but asymptomatic (Grade 1): Continue treatment without dose adjustment, however, study treatment may be discontinued depending on the subject's condition.
- Moderate (Grade 2) condition: Interrupt study treatment (lenvatinib and everolimus) and consider using adrenal cortical hormone. If it is resolved to Grade 0-1 or baseline, resume study treatment at the same dose level as before the interruption. If it does not resolve within 28 days, subject will be treated with

lenvatinib alone after resolving to Grade 0-1 or baseline, according to his/her clinical condition. Investigator will make a decision on whether the subject can resume the treatment and if so, as well as the dose level. Everolimus must not be concomitantly administered.

- Consider using adrenal cortical hormone if Grade 2 lung disease recurs despite of appropriate management. If it is resolved to Grade 0-1 or baseline, resume study treatment at the same dose level as before the interruption. If it does not resolve within 28 days, subject will be treated with lenvatinib alone after resolving to Grade 0-1 or baseline, according to his/her clinical condition. Investigator will make a decision on whether the subject can resume the treatment and if so, as well as the dose level. Everolimus must not be concomitantly administered.
- Severe (Grade 3) condition: Interrupt study treatment (lenvatinib and everolimus) and consider using adrenal cortical hormone. If it is resolved to Grade 0-1 or baseline, resume study treatment with lenvatinib alone after resolving to Grade 0-1 or baseline according to his/her clinical condition. Investigator will make a decision on whether the subject can resume the study treatment and if so, as well as the dose level. Everolimus must not be concomitantly administered.
- If a subject experiences life-threatening (Grade 4) event, both lenvatinib and everolimus must be discontinued.

#### 9.4.8 Management of Infectious Disease

Everolimus is known to decrease immune system activities while increasing the risk of developing infection. Subjects should be closely monitored for signs and symptoms of infections to immediately administer proper medical intervention. Dose adjustment of everolimus may be required. Dose interruptions and reductions of lenvatinib and everolimus will be determined per instructions included in Table 2.

#### 9.4.9 Management of Hyperglycemia and Hyperlipidemia

Hyperglycemia, hyperlipidemia, and hypertriglyceridemia are commonly seen as an adverse reaction in patients treated with rapamycin, including everolimus. Subjects need to have well regulated blood sugar level before being enrolled in the study.

Measurement of blood sugar level will be taken at subject visits as specified in Table 5. If sugar level exceeds standards specified by the study site, measurement should be taken after at least 6 hours of fasting (water is permitted). CTCAE Grade will be given to the sugar level measured at fasted condition. Insulin and/or oral antihyperglycemic drug may be administered (or dose increase if subject is already taking) as needed.

Antihyperglycemic drug will be selected according to individual clinical condition. Concomitant use of everolimus and CYP3A or P-gp inhibitors and inducers (see Appendix 2) should be avoided in accordance with the standard medical procedure.

Dose interruptions, reductions, or discontinuation of lenvatinib and everolimus will be determined per instructions included in Table 2.

#### 9.4.10 Management of Stomatitis

Instruction for daily oral care should be given to subjects prior to study initiation and proper gargling and brushing should be continued throughout the study period. In general, sodium gualenate hydrate is recommended for mouth rinsing and gargling, and mouthwash products containing alcohol, hydrogen peroxide, or iodine should be avoided. For mild to moderate pain, a topical anesthetic such as lidocaine, acetaminophen, or Non-Steroidal Anti-Inflammatory Drugs can be used. To relieve moderate to severe pain, consider using narcotic-analgesic agents.

Dose interruptions, reductions, or discontinuation of lenvatinib and everolimus will be determined per instructions included in Table 2.

#### 9.4.11 Points to Consider on Determination of DLT

1. Grade 4 neutropenia is observed
  - a. Additional tests will be performed as needed to confirm duration of the event.
  - b. If Grade 4 is present on Day 8 and beyond (Day 1 defined as the day the event was confirmed to be Grade 4), the event will be judged as 'duration  $\geq 7$  days'. If the event doesn't resolve and hematology tests cannot be performed on Day 8, the investigator will discuss with sponsor on handling of the event. Consult with independent medical advisor, as needed.
2. Grade 3 or Grade 4 thrombopenia is observed:
  - a. Additional tests will be performed as needed to confirm duration of the event.
  - b. If Grade 3 or 4 continues on Day 8 and beyond (Day 1 defined as the day the event was confirmed to be Grade 3 or 4), the event will be judged as 'duration  $\geq 7$  days'. If the event doesn't resolve and hematology tests cannot be performed on Day 8, the investigator will discuss with sponsor on handling of the event. Consult with independent medical advisor, as needed.
3. Grade 3 or Grade 4 nonhematologic toxicities is observed
  - a. Additional tests will be performed as needed to confirm duration of the event.
  - b. If Grade 3 or 4 continues on Day 8 and beyond (Day 1 defined as the day the event was confirmed to be Grade 3), the event will be judged as 'duration  $\geq 7$  days. If the event doesn't resolve and hematology tests cannot be performed on Day 8, the investigator will discuss with sponsor on handling of the event. Consult with independent medical advisor, as needed.
4. If a subject experiences unexpected AEs that is not listed on 'Table 1 Dose Limiting Toxicity (DLT)' and requires discontinuation from treatment, investigator will discuss with sponsor on handling of the event. Consult with independent medical advisor, as needed.

### 9.4.12 Identity of Investigational Products

Lenvatinib (study drug) will be provided as 4 mg and 10 mg capsules. Each investigational site will purchase commercially available everolimus (concomitant drug) for study treatment. Refer to the most updated prescribing information before administering everolimus to subjects.

#### 9.4.12.1 Chemical Name, Structural Formula of Lenvatinib (E7080)

Test drug code: E7080

Generic name: Lenvatinib Mesilate

[figure not shown]
Chemical name:

4- {3-Chloro-4-[(cyclopropylcarbamoyl)amino]phenoxy} -7-methoxyquinoline-6-carboxamide monomethanesulfonate

Molecular formula:  $C_{21}H_{19}ClN_4O_4 \cdot CH_4O_3S$

Molecular weight: 522.96

Structural formula:

#### 9.4.12.2 Labeling for Study Drug

Both lenvatinib and everolimus will be labeled with the following information. Details are provided in Appendix 4.

[figure not shown]
- For clinical study use only
- Name and address of the sponsor
- Chemical name/drug identifier
- Lot number/batch number
- Storage conditions, expiration date if necessary

#### 9.4.12.3 Storage Conditions

Study drug will be stored in accordance with the labeled storage conditions. Temperature monitoring is required at the storage location to ensure that the study drug is maintained within an established temperature range. The investigator or designee is responsible for ensuring that the temperature is monitored throughout the total duration of the study and that records are maintained; the temperature should be monitored continuously by using either an in-house validated data acquisition system, a mechanical recording device, such as a calibrated chart recorder, or by manual means, such that minimum and maximum thermometric values over a specific time period can be recorded and retrieved as required.

#### 9.4.13 Method of Assigning Subjects to Treatment Groups

1. This is a non-blind study. Study drug will be administered to subjects who were confirmed for eligibility (see Section 9.3) and submitted a written consent form. This study will not be randomized. Procedure for subject enrollment is shown in Figure 2. Unique subject ID numbers prescribed by the sponsor will be assigned to subjects who signed ICF and their names and numbers will be recorded accordingly in the Subject Screening List.
2. Subjects will be screened for enrollment eligibility. The results will be recorded in the Subject Screening List by the investigator or subinvestigator.
3. Subjects' screening results and dispositions will be entered in the subject enrollment form (Appendix 5), which then will be faxed to the subject enrollment center.
4. Once the fax is received, the enrollment center will review subjects' eligibility. If ineligible subject is found, the center will fill in the designated form with details and fax to the investigators who will review the center's assessment, and remove the subject from the study.
5. If missing entries or discrepancies are found on the enrollment form, the center will check with investigators or study coordinator.
6. For subjects who were confirmed for eligibility, the center will fill in the enrollment form with subject ID number, date and dose, and the form will be faxed to investigators.
7. Investigators or study coordinator will review the enrollment form.

**Figure 2 Subject Enrollment Procedure**

9.4.14 Selection of Doses in the Study

See Section 7.5 ‘Study Rationale’ for selection of doses in this study.

#### 9.4.15 Selection and Timing of Dose for Each Subject

See Section 9.4 ‘Study Treatment’ for dose selection and timing for each subject.

#### 9.4.16 Blinding

The study will not be blinded.

#### 9.4.17 Prior and Concomitant Therapy

Any medications (including over-the-counter medications) or therapy administered to the subject during the study (starting at the date of informed consent and for 30 days after the last dose of study treatment) will be recorded on the CRF. The investigator will record on the Adverse Event CRF any AE for which the concomitant medication/therapy was administered. Name of the medication, the starting dose (for treatment of primary disease only), and dates of initial and last administration will be recorded on the CRF.

Medication or fluid infusion administered as pretreatment for surgery, examination, or drug administration will not be considered concomitant drugs. Name of concomitant therapy, dates of initial and last administration will be recorded on the CRF.

#### 9.4.18 Concomitant Therapies

Investigator and subinvestigator will conduct study in compliance with prohibited concomitant drugs and therapies guidelines to ensure subject safety and accurately assess study treatment. Study treatment must be discontinued at once if any prohibited concomitant drug or therapy becomes necessary. Prohibited drug or therapy can be administered to subject per discretion of investigator or subinvestigator giving full attention to subject safety and development of AEs.

##### 9.4.18.1 Prohibited Concomitant Drugs and Therapies

1. Prohibited from the time of subject enrollment for this study until discontinuation from this study
  - a. Anti-cancer therapy other than lenvatinib and everolimus (surgery, anti-cancer medication, endocrine therapy, palliative radiotherapy or immunotherapy, etc.).
  - b. Other investigational drugs.
  - c. Any agent that potentially inhibits CYP3A or P-gp
  - d. Live vaccine (freeze-dried live attenuated rubella, oral poliomyelitis vaccine, freeze-dried BCG, etc.)
2. Prohibited during Cycle 1
  - a. Any agent that potentially or moderately inhibits CYP3A or P-gp, or potentially or moderately induces CYP3A.

#### 9.4.18.2 Limited Use of Concomitant Therapies and Drugs

Drugs that are not prohibited for concomitant use include drugs used to treat complications or AEs or drugs used to ameliorate symptoms (including blood products, blood transfusions, fluid transfusions, antibiotics, steroids, antidiarrheal drugs, and tranquilizers, etc.). These drugs and treatments can be concomitantly used, based on the judgment of the investigator or subinvestigator. In Cycle 2 and onward, agents that potently or moderately inhibit CYP3A or P-gp, and potently or moderately induce CYP3A will be allowed to a limited extent.

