### **Concomitant Drug/Therapy**

The following therapies are **prohibited**:

1. From the time of subject enrollment to off-treatment observation
  - a. Anticancer treatment other than lenvatinib and everolimus (eg, surgery, chemotherapy, endocrine therapy, palliative radiotherapy, immunotherapy).
  - b. Other investigational drugs
  - c. Any agent that potently inhibits CYP3A or P-gp
  - d. Live vaccine (freeze-dried live attenuated rubella, oral poliomyelitis vaccine, freeze-dried BCG, etc.)
2. Cycle 1
  - a. Any agent that potently and moderately inhibits CYP3A or P-gp, or any agent that potently and moderately induces CYP3A

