#### 9.4.18.3 Drug–Drug Interactions

Lenvatinib is a substrate of P-gp and CYP3A, primarily metabolized by CYP3A and aldehyde oxidase while everolimus is a substrate of P-gp and CYP3A, primarily metabolized by CYP3A. Co-administration of drugs that potently or moderately induces CYP3A or P-gp with lenvatinib could affect the metabolism of lenvatinib and everolimus leading to possible development of toxic effect due to increase in plasma concentration. Drugs that potently or moderately induce CYP3A will accelerate metabolism of lenvatinib and everolimus causing decrease in plasma concentration and reduced therapeutic response.

Refer to Appendix 2 for drugs that can impact on activities of drug-metabolizing enzyme CYP3A.

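### Protocol Section 9.4.18.2 allows potent CYP3A/P-gp inhibitors from Cycle 2, although the synopsis and Section 9.4.18.1 ban them for the whole study

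*Protocol*

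**What the plan says.** **The whole-study ban.** Item 1c of the synopsis entry on concomitant therapy prohibits "Any agent that potently inhibits CYP3A or P-gp" from enrollment to off-treatment observation. Item 1c of Section 9.4.18.1 carries the same ban, from enrollment until the subject leaves the study, but prints it as "Any agent that potentially inhibits CYP3A or P-gp".

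**The Cycle 1 ban.** Item 2a of Section 9.4.18.1 prohibits, in Cycle 1 only, "Any agent that potentially or moderately inhibits CYP3A or P-gp, or potentially or moderately induces CYP3A". The synopsis has the same item with *potently* in place of *potentially*.

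**The consequence.** Section 9.4.18 states: "Study treatment must be discontinued at once if any prohibited concomitant drug or therapy becomes necessary". Its next sentence lets the investigator give a prohibited drug at discretion, with attention to safety.

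**The permission.** Section 9.4.18.2 says that in Cycle 2 and later "agents that potently or moderately inhibit CYP3A or P-gp, and potently or moderately induce CYP3A will be allowed to a limited extent". The extent is not defined there.

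**The pharmacology.** Section 9.4.18.3 describes both study drugs as CYP3A and P-gp substrates. It then says: "Co-administration of drugs that potently or moderately induces CYP3A or P-gp with lenvatinib could affect the metabolism of lenvatinib and everolimus". The same sentence goes on to describe the effect as "leading to possible development of toxic effect due to increase in plasma concentration". The following sentence says that drugs inducing CYP3A "will accelerate metabolism of lenvatinib and everolimus causing decrease in plasma concentration and reduced therapeutic response".

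**A further standard.** Section 9.4.9, on hyperglycemia and hyperlipidemia, says that CYP3A or P-gp inhibitors and inducers should be avoided with everolimus. It names no cycle.

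**The concern.** Suppose a subject comes to need a potent CYP3A or P-gp inhibitor in Cycle 2. The synopsis, Section 9.4.18.1 and Section 9.4.18 together tell the site to stop study treatment. Section 9.4.18.2 lets the site continue. The section that should explain the risk does not help, because as printed it assigns raised concentrations and toxicity to inducers and never says that inhibitors raise exposure.

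The first thing at stake is the safety of that subject, who could stay on two substrate drugs with a potent inhibitor on the authority of the protocol. The second is interpretation. Section 9.1 has the sponsor and investigators weigh overall toxicity up to Cycle 2 when they judge tolerability. The synopsis names toxicity up to Cycle 2 that interruption or reduction cannot manage as a reason to consider the 14 mg/5 mg cohort. A toxicity that arose under a potent inhibitor could then be put down to the 18 mg/5 mg dose.

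**Working it through.** No arithmetic applies; this is a comparison of text. The table takes each class of agent and sets the two rules side by side, reading *potentially* as *potently* in line with the synopsis.

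| Agent | Cycle 1 (item 2a) | Cycle 2 on: synopsis and 9.4.18.1 | Cycle 2 on: 9.4.18.2 | Consistent? |
|---|---|---|---|---|
| Potent CYP3A/P-gp inhibitor | Banned | Banned (item 1c) | Allowed to a limited extent | No |
| Moderate CYP3A/P-gp inhibitor | Banned | Not banned | Allowed to a limited extent | Yes |
| Potent or moderate CYP3A inducer | Banned | Not banned | Allowed to a limited extent | Yes |

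The conflict is confined to the first row.

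1. **Can Section 9.4.18.2 be read as an exception to item 1c?** Item 2a already bans potent inhibitors throughout Cycle 1. The only on-treatment period in which item 1c adds anything is therefore Cycle 2 onward, which is the period Section 9.4.18.2 opens up. Read as an exception, it would leave item 1c with no on-treatment effect of its own. The scheme makes sense if potent inhibitors are always banned and the other classes are banned in Cycle 1 only. On that reading, *potently* before *inhibit* in Section 9.4.18.2 is the error.

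2. **Does the discretion sentence in Section 9.4.18 resolve it?** It directly follows the instruction to stop at once, so it most naturally covers giving the needed drug after study treatment has stopped. If it allowed treatment to continue, it would cancel the sentence before it.

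3. **Does Section 9.4.9 resolve it?** No. Advice to avoid inhibitors and inducers is neither a ban with a stop rule nor a limited permission. It is a third standard.

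4. **Which results can be reached?** DLTs are observed in Cycle 1, and PK samples are taken on Cycle 1 Days 1 and 2 and Days 15 and 16 (Table 4). All three classes are banned in Cycle 1, so neither is touched. The judgment on toxicity up to Cycle 2 can be reached. Under Section 9.4.1 no dose reduction is allowed in Cycle 1 without a DLT, and after a DLT reduced dosing resumes only in Cycle 2. Whether reduction can manage a toxicity can therefore only be seen once Cycle 2 has begun.

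5. **The secondary slips.** Section 9.4.18.1 prints *potentially* once in item 1c and twice in item 2a. Taken literally it would widen the ban and the conflict, but the synopsis shows that *potently* is meant. In Section 9.4.18.3, consecutive sentences give opposite effects for inducers. The effect stated in the first, raised concentration, belongs to inhibition, so its *induces* should read *inhibits*.

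**The case against.** The strongest reply is that Section 9.4.18.2 permits and does not require. A site that follows item 1c and stops treatment breaches nothing. The stricter rule is easy to identify: it is stated twice and carries a consequence. The paragraph in Section 9.4.18.2 also opens by speaking of drugs that are not prohibited, and it repeats the scope of item 2a, so it may have been meant only to lift the Cycle 1 restriction. There are other safeguards. Section 9.4.9 advises avoidance, Section 9.4.12 sends sites to the current everolimus prescribing information, and Appendix 2, seen here by title only, lists the relevant drugs.

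The chain to harm is also long. Exclusion criterion 17 removes subjects with a continuing need for such agents. A new need would have to arise in Cycle 2, and the site would have to follow the permissive text. The resulting toxicity would have to resist interruption and reduction, and the reviewers would then have to misattribute it. Drug names, reasons and dates are recorded (Section 9.5.1.7) and listed (SAP Section 5.2.5).

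Much of this stands. A reader might infer that sites are forced into a breach whichever rule they follow; they are not, because the strict rule can always be obeyed. But a permission that a site may decline still authorises what item 1c bans. Exclusion 17 concerns need at entry, while the protocol itself expects infections on treatment, fungal ones included (Sections 7.4 and 9.4.8), so a new drug need can arise later. The medication records let a confounded case be recognised afterwards; they do not tell the site what to do on the day.

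**Conclusion.** Wrong as written: an internal inconsistency in a safety rule, limited to potent CYP3A/P-gp inhibitors from Cycle 2 onward. The effect is on patient safety and conduct in those cycles and, in a case that is probably uncommon, on the attribution of Cycle 2 toxicity in the tolerability judgment.

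No size can be put on it. The documents give neither a rate of need for a potent inhibitor nor a change in exposure. A reader might try to scale the problem by the share of the tolerability window that Cycle 2 occupies, or by the DLT fraction that prompts the lower cohort. The first is calendar time and not risk; the second belongs to the Cycle 1 route, which is unaffected.

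Two other stronger readings are not supported. One is that the DLT result or the dose decision is compromised: DLT counts come from Cycle 1, and the move to 14 mg is a considered judgment, with an independent medical advisor available. The other is that moderate inhibitors and inducers are in conflict too: item 2a limits their ban to Cycle 1.

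The conclusion assumes that *potentially* means *potently*, and that the discretion sentence applies after stopping. The first has the synopsis behind it; the second is the natural reading of the two sentences together.

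**What to change.** In Section 9.4.18.2, delete *potently or* before *moderately inhibit*. From Cycle 2 the permission then covers moderate inhibitors and potent or moderate CYP3A inducers, in agreement with item 1c. If the sponsor's clinicians did intend an exception for potent inhibitors, it must be written into item 1c of the synopsis and of Section 9.4.18.1 instead.

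In the same amendment, change *potentially* to *potently* at the three places in Section 9.4.18.1, and the first *induces* to *inhibits* in Section 9.4.18.3, so that the toxicity risk from inhibitors is stated correctly.

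The cost is a routine wording amendment with no new procedures or data. Because it affects subject safety, Section 11.1 calls for submission to the authorities and IRB approval. The practical downside is that a subject who needs a potent inhibitor after Cycle 1 stops study treatment, which the synopsis and Sections 9.4.18 and 9.4.18.1 already require.
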